PI [name] and Co-I [name] have worked with staff of the Lone Star Chapter of the National MS Society for over 20 years and are well known by MS clinicians throughout the state. The research team has substantial experience with conducting multi-site interventions and data collection (RO1HD035047, R21 NR011076; RO1 NR03195) with persons with MS. Use of the three communities will assure the ability to recruit sufficient participants and support the diversity of the sample (MS predominates in women and whites). Neurologists who are MS Specialists in each community have agreed to assist with recruitment (see letters of support) and serve as consultants for patient referral. The Lone Star Chapter of the National MS Society serves more than 21,000 persons with MS in 174 counties in Texas including these communities.

**SAMPLE:** The sample for this study will consist of persons with physician-diagnosed MS living in the identified Texas metropolitan areas who are concerned about their cognitive problems.

**SAMPLE SIZE:** Power analyses were conducted using data from our recent preliminary study. The initial sample size estimate was based upon an  $f$  value of .38 for the interaction of time by group for the CVLT-Total. The alpha level was set at .01 to account for the multiple analyses that

are proposed to answer the research questions. A minimum sample of 80 was estimated to have 80% power to detect a statistically significant time x experimental group interaction with a .38 effect size. However, we propose to power the study based upon a lower f value of .28, which corresponds more closely to the effect sizes observed for the other neuropsychological tests. Therefore, 180 individuals will be needed to detect an effect size (f) of .28 as statistically significant. This larger sample size will also provide sufficient power for the more complex 3 site nested design. Based on our preliminary study we estimate that 20% of potential participants who respond to recruitment materials will not meet the inclusion criteria and an additional 25-30% will be unable to attend the classes when scheduled. Thus, we will need to screen 320 persons to recruit a sample of 180 participants (60 at each site). Given the number of participants who consent and do not complete the full data collection we will need to recruit up to 230 persons with MS. The number of persons with MS in the 3 communities is more than sufficient.

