**RECRUITMENT AND SCREENING:** Participants will be recruited in a variety of ways including fliers in offices of physicians, targeted mailings to persons with MS on the mailing list of the National MS Society, contact with support groups, notices in MS newsletters and “word of mouth.” Letters of support for recruitment are appended. Recruitment materials will instruct potential participants to call the research office 800 number for additional information about the study. The project staff will have a script to screen potential participants for inclusion/exclusion criteria and will explain the study procedures and requirements to those who are eligible. The Perceived Deficits Questionnaire (Sullivan, Edgley & Dehoux, 1990) will be administered by phone and those scoring indicating they experience at least 5 problems “sometimes” or more often will be eligible to participate. Participants will be asked to provide the name and address of their physician, who will be asked to verify the diagnosis and give a medical clearance for the individual to participate. Recruitment will be ongoing in order to establish a pool of potential participants at each of the three sites. Nine cohorts of 20-22 subjects will be randomly selected (three times at each of three sites) during the study and subjects within the cohort will be randomly assigned (following baseline testing) to the treatment or comparison group. In prior studies, small intervention class sizes (n=10-12) enhanced self-efficacy through vicarious experience and modeling.

Persons who do not qualify to participate in the study based on the screening criteria will be thanked for their interest and receive a brochure from the MS Society on cognitive strategies.

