The group program will consist of weekly 2-hour classes over an 8 week period that present information, guide participants in self-assessment of cognitive problems, resources and barriers to cognitive functioning and enhancing self-efficacy for use of strategies to maximize cognitive functioning. Four major topic areas will be included in the lifestyle change classes (1) Identifying common cognitive problems experienced with MS (2) Compensatory Strategies to Maximize cognitive Skills (3) Maximizing Cognitive Health with a MS – Lifestyle adjustments (e.g. physical activity and energy conservation) to promote cognitive functioning (3) Adjusting to Changes in Cognitive Skills (4) Stress Management (controlling anxiety) and Enhancing Cognition. At each session, the facilitator will evaluate the participants on CACR exercises prescribed at the last session, troubleshoot cognitive strategies and performance difficulties, and prescribe the therapy exercise assignments for the upcoming week.

Computer Assisted Cognitive Rehabilitation (CACR) protocol: In response to the feedback obtained in preliminary studies, we will use the computer training exercises from Lumosity. The computer protocol for this multi-site trial follows:

Computer Protocol: The computer training methodology developed by Lumos Labs, Inc. (San Francisco, CA) uses an open-innovation model targeting effectiveness, designed to adapt to the individual user, offering novel and engaging tasks and challenges within a integrated, hierarchical structure. The Lumosity program has been used in research with childhood cancer

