**Data Analysis:** Inferential analysis will be used to test the study hypotheses. Data analyses will be conducted using SPSS.. Neuropsychological data will be scored by the testers and verified by a second staff member. Data will be entered and checked for accuracy. Internal consistency reliability coefficients for all self-report measures will be assessed with an expectation of alpha = .80 or above. Descriptive analyses will be used to obtain a profile of the sample. The groups will be compared at baseline on demographic and disease variables. Preliminary analysis for tests of assumptions such as normality, independence of errors, homogeneity of variance, and outliers will be conducted to determine if data transformations are necessary.

Missing data are often problematic for randomized controlled trials and various strategies are often used to manage missing data. We will use intention-to-treat strategies to handle missing data. More specifically, a “last observation carried forward” (LOCF) strategy in which missing data points are imputed based on the participant’s existing data.

To account for cohort and city effects, multi-level analyses using SAS Proc Mixed will be conducted and any major effects observed will be included in subsequent analyses. A repeated measures (RM-ANOVA) design will be used to determine time and time by group effects on performance and self-report outcomes. Because of the large variability expected in a community-residing sample of persons with MS, we will use Analysis of Covariance (ANCOVA) to control for the differences among participants that are not germane to assessing the magnitude of the difference attributable to the treatment. Therefore, ANCOVAs will be performed to determine the differences between the intervention group and comparison groups at T2, T3, and T4, after controlling for baseline scores. Separate analyses will be conducted for each outcome measure.

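### Only the intervention arm is taught in classes, but no class term is specified for the RM-ANOVA or ANCOVAs, and any nesting allowance in N=180 is not shown

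*Combined protocol and SAP*

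**What the plan says.** - **Randomisation (Recruitment and Screening).** Nine cohorts of 20-22 are formed, three at each of three sites, and "subjects within the cohort will be randomly assigned (following baseline testing) to the treatment or comparison group". Each cohort therefore contains both arms.
- **Intervention arm (Intervention: MAPSS-MS).** "The group program will consist of weekly 2-hour classes over an 8 week period". At each session "the facilitator will evaluate the participants on CACR exercises prescribed at the last session" and sets the next week's work. The facilitator also phones each participant weekly. Recruitment and Screening gives a reason to expect classmates to influence one another: in prior studies, "small intervention class sizes (n=10-12) enhanced self-efficacy through vicarious experience and modeling".
- **Comparison arm (Comparison Group).** Usual care, a referral to free games and a weekly phone call; no classes.
- **Analysis (Data Analysis).** "To account for cohort and city effects, multi-level analyses using SAS Proc Mixed will be conducted and any major effects observed will be included" (that is, carried into the later analyses). RM-ANOVA is described by time and time-by-group effects. In addition, "ANCOVAs will be performed to determine the differences between the intervention group and comparison groups at T2, T3, and T4", controlling for baseline score. No random-effects structure is given.
- **Power (Sample Size).** At alpha .01, "A minimum sample of 80 was estimated to have 80% power" for f=.38. The final N of 180 is tied to f=.28 without restating the power. Then: "This larger sample size will also provide sufficient power for the more complex 3 site nested design".

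**The concern.** Eight weeks of shared teaching can make classmates' outcomes resemble one another. Here that can happen in the intervention arm only, so the variance of that arm's mean carries a class component that the comparison arm's does not. An analysis that treats participants as independent omits this component.

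The planned multi-level step does not clearly supply it. A cohort effect is shared by both arms and cancels from the arm difference within a cohort. A class effect belongs to one arm of the cohort; statistically it is a cohort-by-arm effect. So even if cohort is kept, the class component remains unmodelled. Whether cohort and city are kept depends on the data, by a criterion the plan does not state.

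At stake are the .01 level, which the plan chose to allow for multiple analyses, and the width of the intervals. Separately, a reader cannot tell whether 180 contains any allowance for nesting.

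**Working it through.** **1. The plan's own sample sizes.** Inputs from Sample Size: alpha .01 (two-sided assumed), power 80%, f=.38 and f=.28, with d=2f for two equal groups.

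Two-group normal formula: N = 4(z.995 + z.80)²/d², with (2.576 + 0.842)² = 11.68.
- f=.38: 46.72/.76² = 80.9, so 81 (82 with equal arms); stated 80.
- f=.28: 46.72/.56² = 149.0, so 149 (150 with equal arms); stated 180.

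F test with noncentrality f²N and independent observations (ranges cover the two choices of error df):

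| Numerator df | Power, N=80, f=.38 | Power, N=180, f=.28 |
|---|---|---|
| 1 | 77% | 87% |
| 2 | 66-68% | 79.5-80.2% |
| 3 | 58-61% | 73-74% |

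The two-group formula reproduces about 80 and leaves 180/150 = 1.20, or about 20% spare, at N=180. The 2-df test reproduces 180 with nothing spare but needs about 100 for f=.38. No calculation tried gives both stated figures.

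**2. Variance with a class effect.** Assumed: 1:1 allocation, nine classes of 10 (half of a cohort of 20), 90 unclustered comparison participants, total variance 1 per arm, no shared cohort variance. The class ICC is not in the documents; .02 / .05 / .10 is assumed.

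True variance relative to that under independence: [(1 + 9·ICC) + 1]/2 = 1 + 4.5·ICC = 1.09 / 1.225 / 1.45.

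Standard error understated by 1 − 1/√ratio = 4% / 10% / 17%.

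**3. Type I error at nominal .01, one unadjusted post-baseline contrast** (simulation, 400,000 runs):

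| Analysis | ICC .02 | ICC .05 | ICC .10 |
|---|---|---|---|
| No cluster term, no shared cohort variance | .013 | .020 | .032 |
| Additive cohort term | .013 | .020 | .034 |
| No cluster term, shared cohort variance .10 left out | .010 | .015 | .026 |
| Paired t test on the nine cohort-level arm differences (8 df) | .010 | .010 | .010 |

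The normal approximation, 2[1 − Φ(2.576/√ratio)], gives .014 / .020 / .032, in agreement with the first row. Row 2 shows that keeping cohort does not cure the problem. Row 3 shows that omitted cohort variance partly offsets it. With no class effect at all, dropping cohort is conservative (about .0084 and .0072 at cohort variance .05 and .10).

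**4. Baseline adjustment.** If baseline correlates .5 with outcome (assumed) and the ICC is on the unadjusted scale, ANCOVA removes individual variance but not class variance. The ratio becomes 1 + 6·ICC = 1.12 / 1.30 / 1.60, with simulated type I error of .015 / .023 / .042 (60,000 runs, no shared cohort variance).

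**5. What the spare N could absorb.** On the two-group reading, 1 + 4.5·ICC = 1.20 gives ICC = .044, or .046 from N=149: about .045. On the 2-df reading it is about zero.

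**The case against.** **Clustering is not ignored.** The plan names a multi-level Proc Mixed step for cohort and city and lists independence of errors among its assumption checks. That stands, and it would be wrong to say the plan overlooks clustering. But neither provision supplies a class or cohort-by-arm term, and step 3 shows that a cohort term alone does not restore the level.

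**The harm depends on an unknown ICC.** This also stands. Prescribed home practice (3 × 45 = 135 minutes a week) exceeds class time (120 minutes), so the class effect may be small. At ICC .02 the unadjusted figures are .010 to .013, and material inflation needs an ICC of roughly .05 to .10.

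**The figures are for single-visit contrasts.** They do not cover the RM-ANOVA time-by-group test. Its size would also depend on the within-person correlation and on whether the class effect changes between visits.

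**A reader might infer that 180 has no room for nesting, or that the trial is underpowered.** The 2-df calculation tempts one to that view. The documents do not support it: they state 80% power only for N=80, the two-group formula comes close to that figure, and on that formula 180 holds about 20% spare. The Sample Size section itself presents the larger N as serving the nested design.

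**Conclusion.** The concern holds in a limited form and should be fixed. The plan specifies no term for a correlation that its own design can produce in one arm, and it makes the retention of cohort and city depend on an undefined criterion. If classmates' outcomes correlate, standard errors are understated: by 4% to 17% for assumed class ICCs of .02 to .10, with the type I error shown above, unless omitted cohort variance offsets it. These figures rest on 1:1 allocation and one class of 10 per cohort. Class size is inferred, since the stated 10-12 describes prior studies.

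On power, the supportable statement is that any nesting allowance is not shown. It could be adequate for a class ICC up to about .045, or it could be nil.

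**What to change.** **Data Analysis.** Delete the rule that keeps only effects seen to be major. For each outcome, prespecify one Proc Mixed model that is kept whatever effects are observed:
- baseline score, arm, time and arm-by-time;
- within-person covariance across visits;
- city, and random cohort within city;
- a random class effect in the intervention arm only (or cohort-by-arm), stating whether it may vary by visit;
- Satterthwaite or Kenward-Roger degrees of freedom.

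Take the arm-by-time test and the T2, T3 and T4 contrasts from this model. State that with nine classes the level is approximate: a single-visit version gave .009 / .011 / .012 at ICC .02 / .05 / .10, and the repeated-measures version was not simulated. Add the cohort-level paired analysis of the nine arm differences as a sensitivity check.

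**Sample Size.** Restate power at N=180 for this model over a stated ICC range, giving class size, numerator df and whether f is baseline-adjusted. The sample size itself need not change.

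**Cost.** Text changes only: the software is already named and class membership will be known. The price is wider intervals, fewer degrees of freedom and a less favourable stated power. For a 1-df single-visit contrast at f=.28, with 10 per class, city in the model and no shared cohort variance, power is about 77% / 70% / 60% at ICC .02 / .05 / .10 with no gain from baseline (82% at ICC 0). It is 88% / 81% / 69% if f is unadjusted and baseline correlates .5 with outcome. The paired check has less power: 61% / 55% / 46% unadjusted. All of these depend on the assumed ICC.

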## **PROTOCOL AND PROPOSED STATISTICAL ANALYSIS:**

This study will test the effects of an intervention (MAPSS-MS) to promote the cognitive functioning of persons with MS. The effectiveness of the intervention will be examined using a prospective, longitudinal, randomized pretest/posttest usual care comparison group design. The intervention consists of an efficacy-building group intervention that will incorporate an individualized computer-based practice component (CACR) to help participants build self-efficacy for skills to improve cognitive functioning and activities of daily living. The group component of the intervention will provide information specific to cognitive difficulties experienced with MS, help participants assess their difficulties and identify strategies to manage cognitive difficulties and improve performance. The group exercises will focus on helping persons translate the skills they are practicing in the CACR component into everyday life to improve overall functioning and health.

Participants will be recruited from three metropolitan communities in Texas: Houston, San Antonio and Dallas/Fort Worth. The Houston metro area has a population of over 5.9 million persons. The population is approximately 26% white/non-Hispanic, 44% Hispanic, 24% Black, and 6% Asian. The San Antonio metro area has a population of 2.2 million persons; 63% are Hispanic and 7% are African American. More than 6.3 million people live in the Dallas/Fort Worth metroplex; 13% are African-American, 4% Asian or Pacific Islander and 21% are Hispanic or Latino of any race. The Lone Star Chapter of the National MS Society has active offices in each community to support recruitment and implementation.

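### The trial is sized on a time-by-group interaction that ignores the baseline equality given by randomisation, and no rule makes the three baseline-adjusted ANCOVAs into one error-controlled test

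*Combined protocol and SAP*

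**What the plan says.** The opening section of the protocol describes a "prospective, longitudinal, randomized pretest/posttest usual care comparison group design". Under RECRUITMENT AND SCREENING, participants are "randomly assigned (following baseline testing) to the treatment or comparison group", so the T1 score is fixed before the arm is known.

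SAMPLE SIZE starts from 80 participants for "80% power to detect a statistically significant time x experimental group interaction with a .38 effect size". It then moves to f = .28 and 180 participants. On the significance level it says: "The alpha level was set at .01 to account for the multiple analyses that" are proposed.

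Data Analysis lists two treatment analyses for every outcome. The first: "A repeated measures (RM-ANOVA) design will be used to determine time and time by group effects on performance and self-report outcomes". The second: "ANCOVAs will be performed to determine the differences between the intervention group and comparison groups at T2, T3, and T4, after controlling for baseline scores". Neither is called primary. PROC MIXED is planned, but only to examine cohort and city effects. No planned test of treatment uses baseline and all three follow-ups together.

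**The concern.** Because randomisation follows baseline testing, the arms have equal true means at T1. An analysis can treat that as known. A time-by-group interaction does not: it asks whether the arm difference departs from its own average over the visits. With T1 among the visits, which is the natural reading of a pretest/posttest design whose follow-ups are labelled T2 to T4, part of a sustained benefit falls into a group main effect that Data Analysis does not list. If the time factor covered T2 to T4 only, a sustained benefit would produce no interaction at all.

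The ANCOVAs use baseline properly, one visit at a time. The plan does not say whether success means all three, any one, or a particular visit, or how they stand beside the interaction. So the test that justifies 180 participants is the less informative of the two, and the more informative analysis has no stated error rate.

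**Working it through.** **Inputs.** N = 180, alpha .01, f = .38 and .28, and 80% power (stated for the f = .38 case) come from SAMPLE SIZE. Equal allocation, 90 per arm, is assumed; cohorts of 20-22 and classes of 10-12 suggest it. The correlation r between visits is not given, so .5 to .9 is shown. Also assumed: unit SD at each visit, equal correlation between all visits, complete data, no clustering by class.

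**1. The plan's own figure.** Noncentral F with noncentrality f²N, at f = .28 and N = 180: .0784 × 180 = 14.1.
- 1 df: power 87%; 80% needs 153 participants.
- 2 df: power 79.5%; 80% needs 180-182.
- 3 df (two arms, four visits): power 73%; 80% needs 200-203.

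So 180 is reproduced by a 2-df test. The figure of 80 for f = .38 is reproduced only by a 1-df normal approximation (82); 2 df gives 99-101. No single choice returns both figures, and the visits, degrees of freedom and correlation behind them are not documented. The comparison below is therefore set at 80% power for the four-visit interaction and not derived from f = .28.

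**2. What the interaction sees.** A benefit d held at T2 to T4 is (0, d, d, d), with mean .75d. The deviations are (-.75, .25, .25, .25)d, with sum of squares (.5625 + 3 × .0625)d² = .75d².

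**3. Noncentrality for a sustained effect**, n = 90 per arm:
- interaction: (n/2)d²/A, where A = (1+2r)/3 + 1 - 2r
- baseline-adjusted joint test of T2, T3 and T4: (n/2)d²/B, where B = (1+2r)/3 - r²

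Both have 3 numerator df. The interaction reaches 80% power at alpha .01 (3 and 534 df) when its noncentrality is 15.6, so d² = 15.6A/45. The joint test then has noncentrality 15.6 × A/B, referred to about 177 denominator df.

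| r | A | B | A/B | d | Joint noncentrality | Joint power | N matching the interaction at 180 (180 × B/A) |
|---|---|---|---|---|---|---|---|
| .5 | .667 | .417 | 1.60 | .481 | 25.0 | 96% | 113 |
| .7 | .400 | .310 | 1.29 | .373 | 20.2 | 91% | 140 |
| .8 | .267 | .227 | 1.18 | .304 | 18.4 | 87% | 153 |
| .9 | .133 | .123 | 1.08 | .215 | 16.9 | 83% | 167 |

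**4. Fading effects**, again with the interaction at 80%. If half the effect is lost by T4, joint power is 94% (r = .5) and 88% (r = .7). If it has gone by T4, joint power is 86% and 83%.

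**5. The planned ANCOVAs.** Under the null, the chance that at least one of three is significant at .01 is about 2.6% per outcome by simulation at r = .5 and .7; the upper bound is 3 × .01 = 3%. With a Bonferroni rule (.01/3 each), power at the same effect sizes is 96% (r = .5, sustained), 92% (r = .7, sustained), 91% (r = .7, fading by half) and 76-77% (r = .7, gone by T4).

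**6. A fixed effect size.** With .4 SD at each of T2 to T4 and r = .3, .5, .7, power is .39, .58, .87 for the interaction; .58, .69, .87 for one ANCOVA; and .92, .94, .99 for a baseline-adjusted average of the three follow-ups.

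**The case against.** The strongest reply is that the interaction is only half of the plan. The ANCOVAs already adjust for baseline, and step 5 shows that with a Bonferroni rule they match or beat the joint test for sustained and half-fading effects. With complete data, or data filled in by carrying observations forward, a joint model estimates the difference at any one visit no more precisely than that visit's ANCOVA. All of this stands. A reader might infer that the trial as a whole would miss a sustained benefit, or that it wastes 40 to 67 of its 180 participants (180 - 140 and 180 - 113). The documents do not support that: those figures measure the interaction alone. What remains is that the Bonferroni rule is not in the plan and the sample size rests on the other test.

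The .01 level might be meant to absorb the three ANCOVAs. It was set with multiple analyses in mind, but the plan does not say which ones or how many.

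A larger power gap can also be produced. With correlation .8 per step between visits and a sustained effect of .40 SD, simulation gives 92% for the joint test against 75% for a Greenhouse-Geisser-corrected RM-ANOVA. Most of that gap is the correction: with an unstructured covariance the interaction itself has about 87% (noncentrality 18.3 against 21.6). In a pattern with baseline weakly and follow-ups strongly correlated, there was no gain (78% against 79%).

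Finally, a significant interaction does not show which arm did better, but neither does a 3-df joint test. Direction comes from the visit-specific differences in either case. The inclusion of T1 in the RM-ANOVA is inferred, not stated.

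**Conclusion.** The point holds as a loss of efficiency in the powered test and the absence of a single error-controlled treatment test. It is not bias, and the interaction does not inflate type I error. For a sustained effect the interaction's 80% compares with 96% at r = .5, falling to 83% at r = .9. The gain shrinks if the effect fades and is small if it has gone by T4. These figures rest on 90 per arm, complete data, equal correlation at an assumed value, no class clustering, and T1 counted as a visit. The change is worth making because it is cheap and settles which test decides, not because the current plan could not detect a benefit.

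**What to change.** For each outcome, make the deciding analysis one repeated-measures model of the T2, T3 and T4 scores with arm, visit, arm-by-visit, baseline and baseline-by-visit, an unstructured covariance, and whatever cohort and city terms the plan retains. Prespecify one arm-effect test at .01. The joint 3-df test that the arm difference is zero at T2, T3 and T4 makes no assumption about its pattern over time. The average over the three visits has more power if the effect is sustained, and has a direction. Choose one in advance. Report the T2, T3 and T4 differences from the same model, and drop the RM-ANOVA interaction as the deciding test. In SAMPLE SIZE, restate power for the chosen test over a range of correlations, with its degrees of freedom.

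Cost: SAP wording, a few lines of PROC MIXED (already planned) and a new power statement; no extra data, visits or participants. The downside is slightly more modelling, and little or no power gain at high correlation, under some correlation patterns, or for effects that vanish by T4.
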